# Table 2: Toxicity Grading Tables – CLINICAL AEs

Clinical AEs	Mild	Moderate	Severe			
	(Grade 1)	(Grade 2)	(Grade 3)			
Diarrhea	2-3 loose or watery stools in a 24-h period.	4-5 loose OR watery stools in a 24-h period.	6 or more loose or watery stools in a 24-h period OR requires IV hydration OR requires medical intervention.			
Oral Discomfort / Dysphagia	Mild discomfort; no difficulty swallowing.	Some limits on eating /drinking.	Eating/talking very limited; unable to swallow solid foods.			
LOCAL IV CATHET	ER REACTION					
IV site reaction	Not applicable.	Erythema with associated symptoms (e.g., edema, pain, induration, phlebitis).	Ulceration or necrosis; severe tissue damage; operative intervention indicated.			
SYSTEMIC REACTIONS						
Anaphylaxis **			Symptomatic bronchospasm, with or without urticaria; parenteral intervention indicated; allergy-related edema or angioedema; hypotension.			
** Definition : A disorder chara like substances from mast cells, dizziness, hypotension, cyanosi	cterized by an acute inflammator causing a hypersensitivity immu s, and loss of consciousness, and	y reaction resulting from the relea ne response. Clinically, it present may lead to death.	ase of histamine and histamine- ts with breathing difficulty,			
Allergic Reaction	Pruritus without rash.	Localized urticaria OR requires oral therapy.	Generalized urticaria OR angioedema OR anaphylaxis OR requires epinephrine			
Hypersensitivity (including drug fever)	Transient flushing or rash; temperature 38.0-38.4°C (100.4-101.1°F).	Rash; flushing; urticaria; dyspnea; temperature 38.5 - 38.9°C (101.2 – 102.0°F).	Symptomatic bronchospasm with or without urticaria; parenteral medication indicated; allergy-related edema or angioedema; hypotension; temperature >38.9°C (>102.0°F).			
Headache	No interference with activity.	Repeated use of non-narcotic pain reliever for more than 24 h OR some interference with activity.	Significant; any use of narcotic pain reliever OR prevents daily activity OR requires triptans.			
Fatigue	No interference with activity.	Some interference with activity.	Significant; prevents daily activity.			

Clinical AEs	Mild (Grade 1)	Moderate (Grade 2)	Severe (Grade 3)			
Myalgia	No interference with activity.	Some interference with activity.	Significant; prevents daily activity.			
SKIN						
Mucocutaneous	Erythema, pruritus.	Diffuse, maculo-papular rash, dry desquamation.	Vesiculation OR moist desquamation OR ulceration.			
Pruritus	No or minimal interference with usual social and functional activities.	Greater than minimal interference with usual social and functional activities.	Inability to perform usual social and functional daily activities.			
ALL OTHER CONDITIONS						
Illness or clinical AE (as defined according to applicable regulations)	Require minimal or no treatment; does not interfere with the subject's daily activities.	Result in a low level of inconvenience or concern with therapeutic measures; may cause some interference with functioning.	Interrupt a subject's usual daily activity and may require systemic drug therapy or other treatment; are usually incapacitating.			

Table 3:	Toxicity	Grading	Tables –	LABOR	ATORY AE
1 4010 01	1 Onicity	Ol wanning	1 460105		II OILI IID.

	Mild	Moderate	Severe
Laboratory AEs	(Grade 1)	(Grade 2)	(Grade 3)
Blood, serum, or plasma	*		
HEMATOLOGY			
Hemoglobin decrease, female – g/dL	9.6 – 11.0	8.0 - 9.5	<8.0
Hemoglobin decrease, male – g/dL	11.0 - 12.9	8.5 - 10.9	<8.5
WBC increase $- x10^3/ \mu L$	>10.8 - 15.0	>15.0-20.0	>20.0
WBC decrease – $x10^{3/} \mu L$	2.4 - <3.4	1.4 - < 2.4	<1.4
Neutrophils decrease – $x10^{3/} \mu L$	1.0 - < 1.4	0.75 - < 1.0	<0.75
Lymphocytes decrease – $x10^{3/} \mu L$	<0.7 –0.4	< 0.4 - 0.3	<0.30
Monocytes increase – $x10^{3/} \mu L$	>0.9 - 2.0	>2.0 - 3.0	>3.0
Eosinophils increase – $x10^{3/} \mu L$	>0.4-0.75	>0.75 - 1.0	>1.0
Basophils increase – $x10^{3/} \mu L$	>0.2-0.5	>0.5 - 0.8	>0.8
Platelets decrease $- x 10^3 / \mu L$	90 - <150	55 - <90	<55
COAGULATION			
PT INR ratio	>1.2 - 1.8	>1.8 - 2.1	>2.1
Prothrombin Time (PT) - seconds	>12.0 - 15.0	>15.0-18.6	>18.6
Activated Partial Thromboplastin Time (APTT) - seconds	>33.0 - 54.0	>54.0 - 75.0	>75.0
CHEMISTRY			
Sodium decrease – mmol/L	130 - 133	124 – 129	<124
Sodium increase – mmol/L	145 - 150	151 - 156	>156
Potassium increase – mmol/L	5.3 - 6.0	6.1 - 6.5	>6.5
Potassium decrease – mmol/L	3.4-3.0	2.5 - 2.9	<2.5
Total Carbon Dioxide (CO 2 ) increase – mmol/L	30 - 35	36 - 37	>37
Total Carbon Dioxide (CO 2 ) decrease – mmol/L	17 - 19	14 - 16	<14
Calcium decrease – mg/dL	7.8-8.6	7.0 - 7.7	<7.0
Calcium increase - mg/dL	10.3 - 11.4	11.5 – 12.5	>12.5
Magnesium decrease – mg/dL	1.2 - 1.5	1.1 - 0.9	<0.9

Laboratory AEs	Mild (Grade 1)	Moderate (Grade 2)	Severe (Grade 3)
Blood urea nitrogen (BUN) increase, 18-39Y - mg/dL	21 - 58	59 – 120	>120
Blood urea nitrogen (BUN) increase, 40-59Y – mg/dL	25 - 58	59 – 120	>120
Glucose decrease, fasting – mg/dL	55 - 69	40 - 54	<40
Glucose increase, fasting – mg/dL	100 - 160	161 - 250	>250
Creatinine increase, male – mg/dL	1.28 - 1.90	1.91 - 3.80	>3.80
Creatinine increase, female – mg/dL	0.58 – 1.50	1.51 - 3.00	>3.00
Direct bilirubin	0.41 - 0.70	0.71 - 1.20	>1.20
Total bilirubin (serum) increase – mg/dL (with other LFTs in the normal range)	1.3 – 2.0	2.1 - 2.5	>2.5
Total bilirubin (serum) increase – mg/dL (accompanied by a >3 x ULN increase in ALT or AST)	1.3 – 1.7	1.8 - 2.4	>2.4
Total protein decrease – g/dL	5.1 – 5.9	4.6 - 5.0	<4.6
Albumin, decrease, Male, 18-30Y - g/dL	4.0 - 3.0	2.0-2.9	<2.0
Albumin decrease, Female, 18-30Y – g/dL	3.8 - 3.0	2.0–2.9	<2.0
Albumin decrease, Male, 31-50Y – g/dL	3.9 - 3.0	2.0-2.9	<2.0
Albumin decrease, Female, 31-50Y – g/dL	3.7 – 3.0	2.0–2.9	<2.0
AST increase – U/L	41 - 80	81 - 120	>120
ALT increase, male – U/L	45-88	89 - 132	>132
ALT increase, female – U/L	33 - 64	65 – 96	>96
Alkaline phosphatase (AP) increase, males 18-20Y – U/L	126 - 250	251 - 375	>375
Alkaline phosphatase (AP) increase, females, 18-20Y – U/L	107 – 250	251 - 375	>375
Alkaline phosphatase (AP) increase, 21-150Y – U/L	122 – 250	251 - 375	>375

#### Table 3: Toxicity Grading Tables – LABORATORY AEs
Laboratory AEs	Mild (Grade 1)	Moderate (Grade 2)	Severe (Grade 3)					
Urine								
URINALYSIS by Dipstick								
Protein	1+	2+	>2+					
Blood (occult)	1+	2+	>2+					
Glucose	1+	2+	>2+					
URINE MICROSCOPY								
Red blood cells (RBC) per HPF	3-10	11-30	>30 and/or gross blood					
White blood cells (WBC) per HPF	6-10	11-30	>30 and/or symptomatic urogenital infection					
Bacteria (microscopic)	few	moderate many						

## Table 3: Toxicity Grading Tables – LABORATORY AEs

Note 1: With the exception of AST, ALT, AP, bilirubin, electrolytes, urine protein, BUN and creatinine, which should be within reference range, lab values of other analytes in the grade 1 range are acceptable for enrollment if (a) they are not considered to be clinically significant by the investigator and (b) there is no cluster of abnormal labs that combined are suggestive of an underlying disorder.

Note 2: Other Exceptions to screening laboratory tests' normal reference ranges are:

- a. Racially based low total WBC or neutrophil counts up to toxicity Grade 1 are allowed, but toxicity Grades 2 or 3 are exclusionary.
- b. Labs performed as part of a panel but not listed above are to be recorded in the database. If abnormal, they are not exclusionary and are not to be graded per Toxicity table, however, the investigator would make a clinical decision about their clinical significance and, if clinically significant, they will be graded according to the criteria in Section 9.2.1. (Examples include mean corpuscular volume (MCV), mean corpuscular hemoglobin (MCH), mean corpuscular hemoglobin concentration (MCHC), red cell distribution width (RDW), mean platelet volume (MPV), and nucleated red blood cell count (NRBC CT), which are included in a CBC with differential.)
- Note 3: If a subject was accepted into the trial with a laboratory value of an analyte that overlaps with values used for grading Grade 1 laboratory abnormalities, a TEAE will be reported if the on-study value of the same analyte increases to Grade 2 or higher.
- Note 4: If the dipstick UA is abnormal, a microscopic UA will be performed, and the results will supersede the results of the dipstick UA.
- Note 5: Menstruating females with a positive dipstick UA or microscopic UA may be retested following cessation of menses.
- Note 6: Isolated laboratory values that are outside the range of eligibility but are thought to be due to an acute condition or due to collection or laboratory error may be repeated once.

ECG interval abnormality	Reference range	Grade 1	Grade 2	Grade 3
QTcF interval prolonged (msec): • Male • Female	•_≤ 450 msec • ≤ 470 msec	Asymptomatic, QTcF • 451 – 479 msec • 471 – 479 msec	Asymptomatic, QTcF 480-500 msec OR increase in interval 30- 59msec above baseline	Asymptomatic, QTcF >500 msec OR increase in interval ≥60 msec above baseline
PR interval prolonged (msec)	≤210 msec	211-250 msec	>250 msec	Type II 2 nd degree AV block OR ventricular pause >3.0 sec

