## 5.1 Subject Inclusion Criteria

All must be answered YES for the subject to be eligible for study participation:

- 1. Subject reads and signs the Informed Consent Form (ICF) and agree to have bronchoscopy with bronchoalveolar lavage under sedation or light anesthesia and comply with study procedures.
- 2. Healthy male or non-pregnant, non-lactating female subjects 18 to 45 years of age (both inclusive) at the time of dosing.
  - a. Note 1: Determined by medical history (MH), medication use, physical examination (PE), and vital signs, clinical laboratory tests and 12-lead ECG within reference ranges at Screening and Day-2. (See Sections 8.1 and 8.2, Appendix B, Table 2, Table 3 and Table 4 and the study-specific MOP.)

Exceptions to BP, HR and laboratory test values being with normal ranges are:

- Abnormal HR and BP on first measurement may be repeated twice more with the subject resting between measurements for at least 5 min according to Section 8.1.6.
- Subjects with baseline  $HR \ge 45$  to 50 bpm may be accepted if otherwise healthy adults with known history of asymptomatic bradycardia.
- Subjects with baseline SBP up to 140 mmHg and DBP up to 90 mmHg may be accepted if otherwise healthy.
- A laboratory value that is Grade 1 will be allowed if not considered to be clinically significant by the investigator, with the exception of ALT, AST, AP, BUN, urine protein, serum creatinine or estimated glomerular filtration rate (eGFR) <70 mL/min /1.73 m^2 by the Chronic Kidney Disease Epidemiology collaboration (CKD-EPI) equation.
- 3. Female subjects of childbearing potential should use highly effective methods of contraception from the time of screening to 30 days after dosing.
  - Note 1: A female is considered of childbearing potential unless post-menopausal (defined as history of ≥1 year of spontaneous amenorrhea and a FSH level >40 IU/L), or permanently surgically sterilized.

- Note 2: Highly effective contraceptive methods include: (a) surgical sterilization methods, such as tubal ligation, bilateral oophorectomy, salpingectomy, hysterectomy, or successful tubal obliteration (e.g., Essure®) with documented radiological confirmation test at least 90 days after the procedure, or (b) long-acting reversible contraception, such as progestin-releasing subdermal implants, copper intrauterine devices (IUDs), levonorgestrel-releasing IUDs.

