#### 9.2.3 Procedures to be Followed in the Event of Abnormal Laboratory Test Values or Abnormal Clinical Findings

A licensed study clinician (listed on FDA Form 1572) will determine seriousness, severity, and causality of abnormal laboratory values; provide a medical evaluation of TEAEs; and classify TEAEs based upon medical judgment.

Abnormal laboratory values or clinical findings for all enrolled subjects after dosing will be assessed using the toxicity scales in Appendix B. Out of range values and findings noted at screening or baseline, but allowable for enrollment and dosing if within Grade 1, will only be considered TEAEs if their severity increases to Grade 2 or higher. For abnormalities noted from the time of study drug dosing, any Grade 1 or higher laboratory abnormality listed on the toxicity Table 3 in Appendix B will be entered in the database as a TEAE. Safety laboratory results that are reported as TEAEs will be evaluated by the CTU clinician as clinically significant (CS) or not clinically significant (NCS). Abnormal laboratory values, performed as part of HEM, COAG, CHEM, or UA but not listed in this toxicity table will be evaluated by the study clinicians, recorded in the source document and, if clinically significant, considered TEAEs and graded according to the criteria in Section 9.2.1.

Protocol-specific laboratory normal range values are included in the study-specific MOP and toxicity grades for evaluation of TEAEs are included in Appendix B, Table 3.

Gross blood in urine that is confirmed due to menses is not a TEAE (but is for all other reasons).

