- 10. The CKD-EPI equation, expressed as a single equation, is  $GFR = 141 \times min(Scr/\kappa, 1)\alpha \times max(Scr/\kappa, 1)-1.209 \times 0.993 Age \times 1.018$  [if female] \_ 1.159 [if black], where Scr is serum creatinine,  $\kappa$  is 0.7 for females and 0.9 for males,  $\alpha$  is -0.329 for females and -0.411 for males, min indicates the minimum of Scr/ $\kappa$  or 1, and max indicates the maximum of Scr/ $\kappa$  or 1 [Levey 2009].(Formula will be used and result will be included in the lab report)
- 11. Urinalysis (UA) by dipstick. If abnormal for blood, protein and glucose, perform microscopic UA. The results of microscopic UA supersede those of UA by dipstick. UA may be postponed in a menstruating female. Abnormal UA in a menstruating female is not graded as a TEAE; the UA should be completed after the end of menstruation.
- 12. Cystatin C in serum.
- 13. Kidney-injury molecule 1 (KIM-1) in urine.
- 14. Ear otoscopy, Valsalva test, tympanometry, stapedial reflexes, and pure-tone audiometry with standard frequencies and distortion product otoacoustic emissions (DPOAEs) at screening. Ear otoscopy, and pure-tone audiometry including high frequencies and DPOAEs at check-in (Day -2 [or Day -4 or Day -3 if needed]) and at Days 3 (+2 days), 14 (± 3 days), and 30 (± 4 days), or ET.
- 15. Subjects will be admitted to the ward on Day -2 after confirmation of eligibility.
- 16. Assignment to Lung PK timepoint cohorts (T1 T5) and Enrollment to be performed before 12-lead ECG on Day -1. Subjects with ECGs on Day-1 and pre-dose on Day 1 with clinically significant abnormalities according to the PI should not be eligible for receiving study drug and should be withdrawn and replaced.
- 17. Subjects may be discharged from the CTU after Day 3 collection of the 60-h plasma PK sample.
- 18. Duration of a ramycin infusion is  $30 \pm 5$  min.
- 19. Adverse events from the start of dosing to the end of the trial are considered treatment-emergent adverse events (TEAE) or serious AEs (SAE).

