### 9.6. Clinical Laboratory Evaluations

Toxicity grading criteria for clinical laboratory results can be found in Table 4. Unscheduled clinical laboratory evaluations will be included in listings but excluded from tabular and graphical summaries, except when calculating the maximum severity post-baseline. Any pre-existing abnormal lab results at Screening and Baseline will be graded and presented in listings but will not be reported as an AE unless it is treatment-emergent (i.e., severity worsens [increases to Grade 2 or higher] after dosing).

The following parameters will be presented (in order):

- CHEM: sodium, potassium, glucose (fasting), BUN, creatinine, eGFR, calcium, chloride, magnesium, total carbon dioxide, albumin, total protein, AP, ALT, AST, total bilirubin, direct bilirubin, TSH, free T4, and free T3
- HEM: hemoglobin, hematocrit, platelets, WBC count, neutrophils, lymphocytes, eosinophils, basophils, and monocytes
- COAG: aPTT, Protime, and INR
- UA: protein by dipstick, glucose by dipstick, occult blood by dipstick, WBC by microscopy, RBC by microscopy, and bacteria by microscopy (microscopy only completed if urine dipstick is abnormal)

All safety laboratory results (CHEM, HEM, COAG, and UA) will be listed in Listing 9, Listing 10, Listing 11, and Listing 12, respectively. Abnormal laboratory results, including results outside of the normal range (ONR), will be listed in Table 23, Table 24, Table 25, and Table 26 for chemistry, hematology, coagulation, and urinalysis, respectively. Abnormal laboratory results that do not have toxicity grading ranges defined in the protocol may not be reported as AEs by the site and will not have severity indicated in tables and listings of abnormal laboratory results, except as ONR.

Laboratory parameters that have grading criteria for both decreases (results lower than normal range) and increases (result higher than normal range) will be summarized separately by direction of change. For example, sodium will be summarized separately as "Sodium, Decrease" and "Sodium, Increase."

Laboratory results will be summarized in tables and figures:

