a. Racially based low total WBC or neutrophil counts up to toxicity Grade 1 are allowed, but toxicity Grades 2 or 3 are exclusionary. b.Labs performed as part of a panel but not listed above are to be recorded in the database. If abnormal, they are not exclusionary and are not to be graded per Toxicity table, however, the investigator would make a clinical decision about their clinical significance and, if clinically significant, they will be graded according to the criteria in Protocol Section 9.2.1. (Examples include mean corpuscular volume (MCV), mean corpuscular hemoglobin (MCH), mean corpuscular hemoglobin concentration (MCHC), red cell distribution width (RDW), mean platelet volume (MPV), and nucleated red blood cell count (NRBC CT), which are included in a CBC with differential.)

Note 3: If a participant was accepted into the trial with a laboratory value of an analyte that overlaps with values used for grading Grade 1 laboratory abnormalities, a TEAE will be reported if the on-study value of the same analyte increases to Grade 2 or higher.

Note 4: If the dipstick UA is abnormal, a microscopic UA will be performed, and the results will supersede the results of the dipstick UA.

Note 5: If the laboratory reports RBC/HPF as a range and not absolute values, then the range 3-10 will be graded as Grade 1. Note 6: Menstruating females with a positive dipstick UA or microscopic UA may be retested following cessation of menses.

Note 7: Isolated laboratory values that are outside the range of eligibility but are thought to be due to an acute condition or due to collection or laboratory error may be repeated once.

	• •			
Vital Sign AEs	Reference Ranges	Mild (Grade 1)	Moderate (Grade 2)	Severe (Grade 3)
Fever - °C Fever - °F	36.1 - 37.2  97.0 - 99.0 	37.3 - 38.4 99.1 - 101.1	38.5 - 38.9 101.2 - 102.0	>38.9 >102.0
Tachycardia - bpm	50 - 100 	101 - 115	116 - 130	>130 or ventricular dysrhythmias
Bradycardia – bpm	50 - 100 - 444	45 - 49	40 - 44	<40
Hypertension (systolic) - mmHg		131 - 150	151 - 160	>160
Hypertension (diastolic) - mmHg	130/89 2,3,4,5	90 - 95	96 - 100	>100
Hypotension (systolic) - mmHg		85 - 88	80 - 84	<80
Tachypnea – breaths per min	10 - 20 	21 - 25	26 - 30	>30
Note 1. No recent hot or col	d beverages or smoking A pr	otocol should select either 	C or  F for inclusion	

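### The rule that microscopy supersedes an abnormal dipstick has no analyte limit, so read literally it removes the grade from dipstick protein and glucose, which microscopy does not measure

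*Protocol*

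**What the plan says.** **The rule.** Protocol Appendix B, Table 3, Note 4 reads: "If the dipstick UA is abnormal, a microscopic UA will be performed, and the results will supersede the results of the dipstick UA". SAP Table 4, Note 4 says the same: "a microscopic UA will be performed, and the results will supersede the results of the dipstick UA". Protocol Table 1, footnote 11, repeated in SAP Table 2, footnote 11, names the triggers and then the consequence: "If abnormal for blood, protein and glucose, perform microscopic UA. The results of microscopic UA supersede those of UA by dipstick".

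**What each test is graded for.** Protocol Table 3 grades the dipstick for protein, occult blood and glucose (1+, 2+, >2+ for Grades 1 to 3). It grades microscopy for RBC per HPF, WBC per HPF and bacteria. SAP 4.5.1 lists the same three microscopy items.

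**Text that treats dipstick protein and glucose as live results.**
- Protocol 5.1, Inclusion Criterion 2 allows Grade 1 laboratory values that are not clinically significant, "with the exception of ALT, AST, AP, BUN, urine protein, serum creatinine" and low eGFR. Table 3 Note 1 also wants urine protein within range at entry.
- Protocol 9.2.3 makes any post-dose Table 3 abnormality of Grade 1 or higher a TEAE. A Grade 1 value already allowed at screening or baseline counts only if it rises to Grade 2 or higher.
- SAP 9.6 presents, among the urinalysis parameters, "protein by dipstick, glucose by dipstick, occult blood by dipstick, WBC by microscopy, RBC by microscopy". Abnormal results by parameter go to Tables 45 and 46, severity grades to Tables 47 and 48, and all urinalysis results to Listing 12.

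**Menses.** Footnote 11 adds "Abnormal UA in a menstruating female is not graded as a TEAE", and says that the urinalysis should be completed once menstruation has ended. Protocol 9.2.3 exempts only gross blood that is confirmed as due to menses.

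**The concern.** A result can sensibly be replaced only by a better measurement of the same thing. RBC per HPF does that for dipstick blood. No microscopy item does it for protein or glucose, yet the rule makes no distinction, and footnote 11 names protein and glucose among the triggers in the sentence just before it says that microscopy prevails.

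Protocol 2.2 reports the kidney as the main target organ in the repeat-dose animal studies, and Protocol 2.6.1 asks for special attention to nephrotoxicity. Urine protein is one of the few analytes for which even Grade 1 is barred at entry. If its dipstick grade can be set aside by a test that does not look for protein, then entry decisions, TEAE entries and the graded urinalysis tables depend on how each site clinician or programmer reads one note.

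**Working it through.** The plan gives no figure to reproduce here. The check compares the analyte lists and then follows one result through the rules.

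**1. Analyte match (Protocol Table 3, SAP Table 4).**

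| Dipstick analyte, graded | Microscopy counterpart, graded |
|---|---|
| Occult blood | RBC per HPF |
| Protein | none |
| Glucose | none |

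Dipstick grade cells: 3 analytes × 3 grades = 9. Cells with no microscopy counterpart: 2 analytes × 3 grades = 6. On the literal rule every abnormal dipstick is superseded, so those 6 of 9 cells cannot stand.

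**2. One result, two readings.** Suppose a subject has dipstick protein 2+ at 24 h and normal microscopy.

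| Provision | Dipstick protein keeps its grade | Note 4 read literally |
|---|---|---|
| Protocol Table 3 | Grade 2 | no grade |
| Protocol 9.2.3 | TEAE | no graded result to enter |
| Protocol 9.5.1 laboratory rule | can count, if related, in the same HLGT in two or more subjects, and unresolved within 48 hours | does not count |
| SAP Tables 47 and 48, protein, Grade 2, 24 h | 1 subject | 0 subjects |

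SAP 6.1 sets the denominator as participants with an available result for that parameter at that timepoint. If all 20 subjects have a urinalysis and only this one is abnormal (an illustration), the table shows 1/20 = 5% on the first reading. On the second it shows 0/20, or 0/19 if the superseded value counts as unavailable. The documents do not say which.

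**3. Entry.** For protein, Inclusion Criterion 2 and Table 3 Note 1 bar Grade 1 and above, but neither says which result decides when dipstick and microscopy differ. For glucose, Grade 1 is already acceptable if not clinically significant, so only Grade 2 or higher is at stake.

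**4. Tests the rule governs.** Urinalysis is scheduled at Screening, Day -2, Day 1 pre-dose, 24 h, 48 h and Day 14. For 20 enrolled subjects:
- eligibility (Screening and Day -2): 2 × 20 = 40
- baseline (Day 1 pre-dose): 1 × 20 = 20
- post-dose: 3 × 20 = 60

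These are tests to which the rule applies. Only those with an abnormal dipstick protein or glucose would be changed by it.

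**5. What else covers the kidney.** Creatinine and BUN have Table 3 grades and are unaffected. eGFR, cystatin C and KIM-1 are also unaffected but have no Table 3 grade. KIM-1 is not collected at 24 h (Protocol 8.2.8.2), so urinalysis is the only scheduled urine test of the kidney at that time.

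**The case against.** The best reply is that the specific provisions outrank a general note. Table 3 grades dipstick protein and glucose, Protocol 9.2.3 turns those grades into TEAEs, and SAP 9.6 lists them as parameters beside microscopy. Nothing in the text of SAP 9.6 drops a dipstick value once microscopy is done. A reading that empties all these provisions is not the natural one, and a sensible site would apply the rule analyte by analyte. Raw results remain in Listing 12, and clinicians still judge abnormal findings under Protocol 9.2.3.

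Much of this stands. A reader might infer that proteinuria and glycosuria are erased from eligibility and from the safety results, or that a volunteer with proteinuria would be admitted. The documents do not support that. The admission claim needs the site to set aside both Inclusion Criterion 2 and Table 3 Note 1, which sits in the same block of notes as Note 4. Nor is this a trial built around nephrotoxicity: the primary objective is plasma and lung PK, safety is secondary and kidney biomarkers are exploratory. The halting effect is also remote, since several conditions must hold together.

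The reply does not settle the matter, though. SAP 9.6 refers to SAP Table 4 for grading, and Note 4 is attached to that table. Footnote 11 names protein and glucose as triggers, so a blood-only reading has no support in its wording. The contrary provisions therefore show a conflict; no passage resolves it.

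On menses, footnote 11 defers the test and Table 3 Note 5 allows retesting, so that mismatch is smaller.

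**Conclusion.** The point holds as an over-broad rule that conflicts with other parts of both documents. All four statements of the rule let microscopy replace any abnormal dipstick, while graded microscopy re-measures only blood. Taken literally, 6 of 9 dipstick grade cells are void, against Inclusion Criterion 2, Table 3 Note 1, Protocol 9.2.3 and SAP 9.6 with Tables 45 to 48. Two competent programmers could produce different urinalysis tables from the same data.

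The practical size is unknown. It depends on how often dipstick protein or glucose is abnormal with clean microscopy, and on which reading is applied. A reader might take the 120 scheduled urinalyses as the number affected; they are only the tests governed, and just 40 of them bear on eligibility. The primary PK objective and creatinine, BUN, eGFR, cystatin C and KIM-1 are not affected.

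The menses wording is a minor, separate mismatch: footnote 11 leaves any abnormal urinalysis ungraded, whichever analyte is abnormal, while Protocol 9.2.3 exempts only gross blood confirmed as due to menses.

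**What to change.** Change the rule in all four places: Protocol Table 3 Note 4, Protocol Table 1 footnote 11, SAP Table 2 footnote 11 and SAP Table 4 Note 4. Changing fewer would leave the contradiction in force.

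- State that microscopy supersedes only the analyte it re-measures, so that RBC/HPF replaces dipstick occult blood.
- State that dipstick protein and glucose are graded and tabulated on the dipstick whatever the microscopy shows, as Table 3 and SAP 9.6 already provide. The entry criterion and the halting rule themselves need no change.
- Reconcile footnote 11's menses wording, in both documents, with Protocol 9.2.3.

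The cost is one sentence in four places plus the menses wording. No test, visit or sample is added. A few more Grade 1 urinalysis TEAEs may be reported. The change should be made before urinalysis results are graded for the final tables.
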